9.4.3.1.5 Time to response

Time to response (TTR) is defined as the time from the date of first dose until the date of the first documented response (which should be subsequently confirmed if it's a partial response), as determined by independent central review and investigator per REiNS criteria.

9.4.3.2 Disfigurement

Detailed recommendations for photography techniques are provided in the photography manual.

9.4.4 Calculation or derivation of clinical outcome assessment variables

9.4.4.1 Pain

9.4.4.1.1 FLACC pain scale (3 years)

The FLACC pain scale will be assessed as scheduled in Table 1. Change from baseline will be derived for each visit.

CONFIDENTIAL AND PROPRIETARY 87 of 183

9.4.4.1.2 Faces pain scale – revised (4 to 17 years)

The Faces pain scale will be assessed as scheduled in Table 1. Change from baseline will be derived for each visit.

9.4.4.1.3 NRS-11 (adult cohort)

The NRS-11 consists of 4 questions scored on an 11-point scale 0=no pain to 10=worst pain you can imagine. The primary outcome for the self-reported NRS-11 will be the rating of one specific tumour pain (e.g. the "target tumour"). This pain rating will be the physician-selected target tumour.

9.4.4.1.4 Pain interference index

The PII is a 6-item scale that assesses the extent to which pain has interfered with an individual's daily activities in the past 7 days. Items are rated on a 7-point Likert scale (0=not at all to 6=completely), and the total scale is the mean of the completed items. The total scale will be computed if at least 50% of items are answered (e.g. 4 out of 6).

9.4.4.2 Health-related quality of life

9.4.4.2.1 PedsQL (paediatric cohort)

The generic PedsQL consists of 23 questions and yields a total score. The 4 subscales are: 1) physical functioning (8 items), 2) emotional functioning (5 items), 3) social functioning (5 items), and 4) school functioning (5 items). Each item is scored on a 5-point Likert scale (0=never a problem; 1=almost never a problem; 2=sometimes a problem; 3=often a problem; 4=almost always a problem). For self-reported and parent/guardian reported separately, items are reverse-scored and linearly transformed to a 0 to 100 scale (0=100, 1=75, 2=50, 3=25, 4=0), so that higher scores indicate better HRQoL. Scale scores are computed as the sum of the items divided by the number of items answered (this accounts for missing data). A Total Scale Score will also be derived as the sum of all the items divided by the number of items answered on all the scales. If more than 50% of the items in the scale are missing, the scale score is not computed (Nutakki et al 2018). In addition, scale scores will be calculated using the raw item scores (without the linear transformation, but still reversed).

The primary outcomes for HRQoL will be the Total Scale Score of the self-reported PedsQL for children \geq 5 years of age and the Total Scale Score of the parent PedsQL administered to parents of children 3 to 4 years of age.

Secondary outcomes for HRQoL will be the mean scores of the 4 domains (physical, emotional, social, and school) of the self-reported scale completed by children >5 years of age and the 4 domain mean scores from the parent-reported scale given to parents of children 3 to 4 years of age.

9.4.4.2.2 EORTC QLQ-C30 (adult cohort)

The EORTC QLQ-C30 consists of 30 questions that can be combined to produce 5 functional scales (physical, role, emotional, cognitive, and social), 3 symptom scales (fatigue, pain, and nausea/vomiting), 5 individual items (dyspnoea, insomnia, appetite loss, constipation, and diarrhoea), and a global measure of health status. The EORTC QLQ-C30 will be scored according to the EORTC QLQ-C30 Scoring Manual. An outcome variable consisting of a score from 0 to 100 will be derived for each of the symptom scales/symptom items, each of the functional scales, and the global health status scale in the EORTC QLQ-C30 according to the EORTC QLQ-C30 Scoring Manual. Higher scores on the global health status and functioning scales indicate better health status/function, but higher scores on symptom scales/items represent greater symptom severity.

9.4.4.2.3 PlexiQoL (adult cohort)

The PlexiQoL consists of several questions that are each answered as "true" if the statement applies or "false" if the statement does not apply. The time frame for the assessment is "at the moment." These statements assess whether the subject avoids crowds, are unable to join activities with family and friends, etc.

9.4.4.3 Physical functioning

Physical functioning will be assessed as scheduled in Table 1 using the PROMIS measures for mobility and upper extremity. Both raw and T-scores will be analysed separately. Higher scores indicate better physical functioning.

9.5 Statistical analyses

Analyses will be performed by AstraZeneca or its representatives. A comprehensive statistical analysis plan (SAP) will be developed and finalised before database lock and will describe the subject populations to be included in the analyses, and procedures for accounting for missing, unused, and spurious data. This section is a summary of the planned statistical analyses of the primary and secondary endpoints. Any deviations from this plan will be reported in the CSR.

Same DCOs would be applied for both analysis of pediatric cohort and adult cohort. Primary DCO in this study will take place when the last subject dosed has had the chance to complete their visit at the end of cycle 10. Final DCO will occur when the last subject dosed has had the chance to complete their visit at the end of cycle 24. In addition, an interim analysis will be conducted when last subject dosed has had the chance to complete their visit at the end of cycle 4 to assess PK, safety, tolerability and efficacy in Chinese subjects with NF1 and inoperable PN.

Data from the paediatric and adult cohorts will be analysed separately. In general, baseline is defined as the last assessment before the first dose of selumetinib. Demographic data and baseline subject characteristics will be analysed for the safety analysis set. PK will be analysed based on the PK analysis set. Efficacy, clinical outcome assessment, exposure and safety data will be analysed based on the safety analysis set.

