- ^t Tumour assessments will be performed at screening and every 4 cycles (16±1 weeks) up to the end of Cycle 24 (i.e. at the end of Cycles 4, 8, 12, 16, 20, and 24). From the end of Cycle 24, tumour assessments will be performed every 6 cycles (24±1 weeks) as long as the subject remains on study treatment or until disease progression. Subjects who discontinue study treatment due to reasons other than disease progression will continue to undergo tumour assessments for approximately 1 year, if clinically applicable, and the assessment schedule should continue per the regular tumour assessment interval.
- ^u Disfigurement assessments will be performed at screening and at the end of Cycles 8, 16 and 24 as long as the subject remains on study treatment.
- ^v Baseline clinical outcome assessments should be performed prior to and as close to the first dose of selumetinib as possible (PGIC should not have any baseline assessments). Post-baseline assessments should be performed at the end of each cycle up to the end of Cycle 4, every 2 cycles up to the end of Cycle 12, every 4 cycles up to the end of Cycle 24, and every 6 cycles thereafter, as long as the subject remains on study treatment. In the pediatric cohort, the pain medication survey will be completed on paper by the parent. In the adult cohort, the pain medication survey will be completed on paper by the patients. Other assessments will be performed electronically using on-site tablets.

- * Adults and children from 8 to 17 years of age will complete self-reported PII; parents/legal guardian of children from 5 to 17 years of age will complete the parent proxy PII.
- Subject-reported versions are for subjects aged 5 to 7 years, 8 to 12 years, and 13 to 17 years. In addition, the corresponding parent-reported versions will also be included. For subjects 3 to 4 years of age, only the parent-reported version will be included.
- ^y Self-reported short forms will be administered to children from 8 to 17 years of age and parallel parent proxy forms to children aged from 5 to 17 years. In the adult cohort, a newly developed PROMIS short form physical functioning scale will be used.
- ^z Will be parent-reported for children aged up to 17 years and self-reported for children aged 8 to 17 years and adults.

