PNs in NF1 patients are histologically benign Schwann-cell tumours (Wu et al 2005; Rutkowski et al 2000) that, depending on the location and the growth rate, bear all the characteristics typical of cancers. There is a high unmet medical need for patients with NF1 and inoperable PN as there are no approved medical treatments to cure, prevent or reverse the disease. A number of medical treatments have undergone evaluation in early clinical studies for subjects with NF1-related PNs, but these studies have reported only moderate to no clinical activity, and no systemic therapy has been shown to induce consistent and durable tumour shrinkage. Since these relentlessly growing tumours induce co-morbidities that impact children from early childhood through adolescence and their entire lifespan, patients with inoperable and progressive PNs suffer from a significant unmet medical need. There are no epidemiological data to estimate the actual incidence or prevalence of NF1 in China. It is believed that the clinical picture of NF1, including NF1 and inoperable PN, in China is in line with that observed globally. Debulking surgery, which is complex and difficult, is the only available treatment for suitable patients with PN, who are always in a distressing condition both physically and mentally. Only a few patients may eventually receive surgery. There is therefore a significant unmet medical need for patients with NF1 and inoperable PN in China.

In the clinical setting, treatment with selumetinib in the Phase 1 SPRINT study resulted in confirmed partial responses (PRs; tumour volume decreases from baseline of \geq 20%) in 16/24 (66.7%) children. The response rate was confirmed in SPRINT Phase II Stratum 1. The overall response rate by NCI POB central analysis was 66% (95% CI: 51.2, 78.8; 33/50 patients). Median time to response is 8 cycles. For responders, 42.4% (14/33 patients) achieved response at cycle 5, 72.7% (24/33 patients) achieved response at cycle 9, 97% (32/33 patients) achieved response at cycle 13. Importantly, improvements in PN-related pain and motor impairment demonstrated that selumetinib provided clinical benefit. Selumetinib, therefore, has promising clinical activity for the treatment of NF1 and inoperable PN, as well as a favourable safety profile.

A detailed description of the chemistry, pharmacology, efficacy, and safety of selumetinib is provided in the Investigator's Brochure.

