- Identify and select the inoperable target PN (plus a maximum of 1 additional nontarget PN) for 3D MRI evaluation. Should there be more than 2 inoperable PNs that meet the criteria for selection, the 2 most clinically relevant PNs will be followed by 3D MRI analysis.
- Perform MRI sequences on the selected index lesions as outlined in the MRI acquisition protocols.

On study imaging evaluation:

Unless clinically indicated otherwise, and as defined in Table 1, 3D volumetric MRI of the target and nontarget PNs should be performed at every 4 cycles (16 ± 1 weeks) relative to the date of first dose for the first 2 years (24 cycles). From the end of Cycle 24, tumour assessments will be performed every 6 cycles (24 ± 1 weeks), as long as the subject remains on study treatment or until disease progression. Subjects who discontinue study treatment due to reasons other than disease progression will continue to undergo tumour assessments for

approximately 1 year, if clinically applicable, and the assessment schedule should continue per the regular tumour assessment interval.

- Complete response (CR): disappearance of the target lesion.
- PR: decrease in the volume of the target PN by 20% or more compared to baseline. The PR is considered unconfirmed at the first detection and confirmed when observed again at a consecutive scan within 3 to 6 months.
- Stable disease: insufficient volume change to qualify for either PR or PD.
- PD: increase in the volume of the target PN by 20% or more compared to baseline or the time of best response after documenting a PR. The appearance of new PN (with the exception of new discrete subcutaneous neurofibromas as noted below) or unequivocal progression of an existing nontarget PN is also considered PD. In this study unequivocal progression is defined as an increase in the volume of the non-target PN by 20% or more compared to baseline.

The clinical appearance of new discrete subcutaneous neurofibromas does not qualify for disease progression. Worsening of existing symptoms or the appearance of new symptoms that persist for more than 7 days and that are felt to be definitely related to the PN should be evaluated by repeating the MRI. Subjects should not be classified as having PD solely on the basis of new or increased symptoms

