9.4.3 Calculation or derivation of efficacy variables

9.4.3.1 Tumour response

9.4.3.1.1 Objective response rate

Objective response rate (ORR) is defined as the proportion of subjects who have a CR or confirmed PR (defined as target PN volume decrease $\geq 20\%$ compared to baseline and confirmed by a consecutive scan within 3 to 6 months after first response), as determined by independent central review and investigator per REiNS criteria.

Best overall response (BOR) is defined as the best response recorded from the start of the treatment until progression or the last evaluable MRI assessment in the absence of progression.

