9.6 Interim analyses

Same DCOs would be applied for both analysis of pediatric cohort and adult cohort. In addition, an interim analysis will be conducted when last subject dosed has had the chance to complete their visit at the end of cycle 4 to assess PK, safety, tolerability and efficacy in Chinese subjects with NF1 and inoperable PN.

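### The primary data cut-off at the end of Cycle 10 falls between the Cycle 8 and Cycle 12 scans, so confirmed ORR at that cut is biased low for late-dosed subjects, by an amount set by accrual

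*Protocol*

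**What the plan says.** Sections 1.2, 4.4 and 9.5 of the protocol set one primary cut-off for both cohorts, "when the last subject dosed has had the chance to complete their visit at the end of cycle 10". The final cut comes at the end of Cycle 24 of the last subject. Section 9.6 adds that "an interim analysis will be conducted when last subject dosed has had the chance to complete their visit at the end of cycle 4", with efficacy among its purposes.

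Table 1, footnote t, fixes the imaging: "Tumour assessments will be performed at screening and every 4 cycles (16±1 weeks) up to the end of Cycle 24", that is, "i.e. at the end of Cycles 4, 8, 12, 16, 20, and 24". No scan is scheduled at Cycle 10.

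Section 8.1.1 states: "The PR is considered unconfirmed at the first detection and confirmed when observed again at a consecutive scan within 3 to 6 months". Section 9.4.3.1.1 carries the same rule into ORR, where a PR must be "confirmed by a consecutive scan within 3 to 6 months after first response". Section 9.5.3 analyses efficacy on the safety analysis set, so every treated subject is in the denominator.

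On expected timing, section 2.2 reports that of the SPRINT Phase II Stratum 1 responders "42.4% (14/33 patients) achieved response at cycle 5, 72.7% (24/33 patients) achieved response at cycle 9", and 32 of 33 by cycle 13, with a median time to response of 8 cycles. The Amendment 2 rationale says that the cut-offs were revised on SPRINT results and will give sufficient safety and efficacy data.

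**The concern.** For the subjects with the least follow-up, a cut at Cycle 10 holds no more scheduled tumour data than a cut at Cycle 8. They have two post-baseline scans, so only a PR first seen at Cycle 4 can be confirmed. One first seen at Cycle 8 is scored as a non-response, although the scan that could confirm it is due 8 weeks later. Duration of response and time to response also depend on a confirmed response, so they lose the same subjects.

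The risk is to interpretation. A confirmed ORR from 16 subjects per cohort, reported at the primary cut beside the 66% cited in the background, could look like a weaker effect in Chinese subjects when part of the difference is follow-up. The Cycle 4 interim has a sharper form of the problem: the last-dosed subjects have one post-baseline scan and cannot have a confirmed PR.

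**Working it through.** **Protocol figures reproduced.** 33/50 = 66.0%, with a Clopper-Pearson 95% interval of 51.2% to 78.8%, as stated. 14/33 = 42.4%, 24/33 = 72.7% and 32/33 = 97.0%, as stated.

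**Calendar.** In Table 1 the end of Cycle k is study day 30 + 28 × (k − 1). This gives Cycle 4 = day 114, Cycle 8 = 226, Cycle 10 = 282, Cycle 12 = 338, Cycle 16 = 450 and Cycle 20 = 562.

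- Cycle 8 to Cycle 12: 338 − 226 = 112 days, or 3.7 months, inside the 3-to-6-month confirmation window.
- Cycle 8 to Cycle 10: 282 − 226 = 56 days, or 1.8 months. An unscheduled scan at Cycle 10 would be too early to confirm.
- Cycle 10 to Cycle 12: 338 − 282 = 56 days. The ±7-day windows do not bridge this gap (latest Cycle 10 visit day 289, earliest Cycle 12 scan day 331).

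The subjects affected are therefore those dosed less than about 56 days before the last subject of either cohort.

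**Ceiling for one subject.** Assume that SPRINT cycles 5, 9 and 13 correspond to the ends of Cycles 4, 8 and 12 here, that the paediatric timing applies to both cohorts, and that every response is confirmed at the next scan. The probability that a subject shows a confirmed response is then:

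- last scan Cycle 8: 14/50 = 28%
- last scan Cycle 12: 24/50 = 48%
- last scan Cycle 16: 32/50 = 64%
- last scan Cycle 20 or later: 33/50 = 66%

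First responses at Cycle 8 are 24 − 14 = 10 of 33 responders (30%), or 10/50 = 20% of subjects, about 3 in 16.

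**Expected cohort ORR.** Section 4.5 opens further enrolment only after the first 6 subjects of a cohort have had about 3 cycles (84 days). I placed the last of those 6 subjects 84 days before the first of the other 10, spread the other 10 evenly over S days, and spread the first 6 over 0.6 × S days. Expected ORR is the sum of the per-subject numerators above divided by 16 × 50 = 800. The spreads are assumptions.

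| Accrual | Lacking Cycle 12 scan at the Cycle 10 cut | ORR at Cycle 10 cut | ORR at Cycle 12 cut |
|---|---|---|---|
| Gated, S = 0 | 10 of 16 | (6×24 + 10×14)/800 = 35.5% | 16×24/800 = 48.0% |
| Gated, S = 56 | 9 of 16 | (1×32 + 6×24 + 9×14)/800 = 37.8% | (6×32 + 10×24)/800 = 54.0% |
| Gated, S = 112 | 5 of 16 | (6×32 + 5×24 + 5×14)/800 = 47.8% | (3×33 + 4×32 + 9×24)/800 = 55.4% |
| Gated, S = 252 | 2 of 16 | (6×33 + 4×32 + 4×24 + 2×14)/800 = 56.3% | (8×33 + 4×32 + 4×24)/800 = 61.0% |
| Even over 52 weeks, no hold | 3 of 16 | (4×33 + 5×32 + 4×24 + 3×14)/800 = 53.8% | (6×33 + 5×32 + 5×24)/800 = 59.8% |

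The move from Cycle 10 to Cycle 12 is worth 5 to 16 percentage points in these scenarios. The rest of the distance to 66% comes from responses first seen at Cycle 12 or later, which a Cycle 12 cut also leaves unconfirmed in late subjects.

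**The case against.** Four arguments weigh against the point.

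1. **Most subjects may be unaffected.** The trigger concerns the last subject dosed. The safety review gate puts at least the first 6 of 16 per cohort past Cycle 12, and the common cut-off gives extra follow-up to whichever cohort fills first. The synopsis estimates first enrolment in Q4 2020 and last completion in Q4 2023. If completion means about the Cycle 24 visit (day 674), accrual lasts roughly 11 to 17 months. This is an inference from estimated dates, but it favours the 52-week row, where the gap is about 6 points, or one subject in 16. The exact interval for 9/16 is 30% to 80%, far wider than that. This stands, and it limits the size.
2. **The cut is not set for ORR.** Safety, tolerability and PK are primary, no hypothesis is tested, no comparison with 66% is specified, and the Cycle 24 cut recovers the missing confirmations. This stands and lowers the severity.
3. **Any early cut truncates confirmation.** This is true, and Cycle 12 is not a full cure. But Cycle 10 is the weaker choice for response, because for the last subjects it waits 8 weeks beyond the Cycle 8 scan without gaining a scan.
4. **The data will be visible anyway.** Section 9.5.3 already plans volume-change summaries, waterfall plots and individual plots, and further tabulations could sit in the SAP. This is partly right. Those displays would show a 20% shrinkage at Cycle 8, but they do not change the ORR and interval reported. The cut-off itself is fixed in the protocol.

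Two stronger readings should be resisted. A reader might infer that no Cycle 8 response can be confirmed at the primary cut, but anyone dosed about 56 days or more before the last subject already has the Cycle 12 scan. A reader might also take 28% as the expected cohort ORR. That is one minimum-follow-up subject's ceiling, and the enrolment gate rules it out for a cohort.

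**Conclusion.** The point holds for subjects dosed within about 56 days of the last subject in either cohort. For them, a PR first seen at Cycle 8 cannot be confirmed by the primary cut, yet they remain in the denominator. Confirmed ORR at that cut is therefore biased low. The direction follows from the protocol's own text. The size depends on accrual, which the protocol does not state: about 36% to 56% at Cycle 10 against 48% to 61% at Cycle 12 under gated accrual, and about 54% against 60% with even accrual over 52 weeks.

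These sizes rest on SPRINT paediatric timing for both cohorts, on reading cycles 5, 9 and 13 as the Cycle 4, 8 and 12 scans, on every response being confirmed, and on the assumed spreads. The scan arithmetic is firm; the percentages are illustrative. It would be wrong to attribute the whole distance to 66% to the choice of Cycle 10, since part of it is later first responses.

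Severity is should-fix. ORR is secondary and descriptive, and the final cut repairs it. The matter still deserves a change, because Amendment 2 presents the cut as sufficient for efficacy on SPRINT results, while those results place 30% of responders' first responses at the scan that a Cycle 10 cut cannot confirm in late subjects.

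**What to change.** Preferred: align the primary data cut-off with the Cycle 12 scan of the last subject dosed, in sections 1.2, 4.4 and 9.5. The cost is 8 weeks, with no added scans or subjects. Every subject then has the opportunity for a confirmatory scan after a Cycle 8 response.

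If Cycle 10 is kept for PK and safety, report beside the all-subject confirmed ORR:

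- confirmed ORR among subjects whose first-dose date gave them the chance to reach the Cycle 12 scan by the cut, whether or not they are still on treatment, so that the subset is defined by opportunity and not by outcome;
- confirmed plus unconfirmed PR for all subjects.

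Name the Cycle 24 cut as the definitive ORR. This alternative costs only wording and two summary lines.

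At the Cycle 4 interim, report percentage volume change and unconfirmed PR as the efficacy measures, because the last-dosed subjects cannot yet have a confirmed PR.

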9.5.1 Pharmacokinetic analyses

Plasma concentrations will be listed and summarised by cohort, analyte, dose level (if applicable), and nominal sample time using the following summary statistics:

- The G_{mean} (calculated as exp [μ], where μ is the mean of the data on a logarithmic scale).
- Geometric coefficient of variation (GCV) calculated as 100√(exp(s²)-1), where s is the SD of the data on a log scale.
- $G_{mean} \pm SD$ (calculated as $exp[\mu \pm s]$).
- Arithmetic mean calculated using untransformed data.
- SD calculated using untransformed data.
- Coefficient of variation (CV; % CV calculated using untransformed data).
- Median.
- Minimum.
- Maximum.
- Number of observations.
- Number of observations below the lower limit of quantification (LLOQ; n below LLOQ).

The derived PK parameters except t_{max} will be summarised by cohort, analyte, and dose level (if applicable) using the following summary statistics:

- G_{mean} (calculated as exp [μ], where μ is the mean of the data on a logarithmic scale).
- GCV (calculated as $100\sqrt{(\exp(s^2)-1)}$, where s is the SD of the data on a log scale).
- $G_{mean} \pm SD$.
- Arithmetic mean calculated using untransformed data.
- SD calculated using untransformed data.
- CV (% CV, calculated using untransformed data).
- Median.
- Minimum.
- Maximum.

CONFIDENTIAL AND PROPRIETARY 90 of 183

• Number of observations.

The following summary statistics will be presented for single dose and/or steady state t_{max}:

- Median.
- Minimum.
- Maximum.
- Number of observations.

Dose/BSA-normalised PK parameters for selumetinib and its metabolite (N-desmethyl selumetinib) will be summarised as appropriate.

The PK data or dose/BSA-normalised PK parameters for selumetinib and its metabolite (N-desmethyl selumetinib) after a single dose and multiple doses, respectively, will also be displayed graphically. Displays may include plasma concentration subject profiles (on the linear and log-scale) versus time and G_{mean} concentration (on the linear and log-scale) versus time. Scatter plots of PK parameters may also be presented as appropriate.

